#### **MCI Patient-specific Inclusion Criteria**

Clinical diagnosis of MCI made by a specialist\* in a patient who fulfils the established clinical consensus criteria for MCI [NIA/AA 2011] specifically:

- Concern regarding a change in cognition compared to the person's previous level, by the patient and/or informant

- Objective evidence of impairment of one or more cognitive domains, greater than expected for age, and educational background, over time if repeated measures are available.
- Preserved independence of functional abilities and minimal to no impairment on complex instrumental functions
- Not demented

#### **Vascular Dementia Specific Inclusion Criteria**

Clinical diagnosis of VascD made by a specialist\* in a patient who fulfils the NINDS-AIREN criteria for VascD, specifically:

- Cerebrovascular disease defined by the presence of focal signs on neurological examination consistent with stroke and evidence of cerebrovascular disease on brain imaging.
- One or more of:
  - Onset of dementia within 3 months of a diagnosed stroke
  - Abrupt deterioration in cognitive function
  - Fluctuating, stepwise progression of cognitive deficits

#### **Alzheimer's Dementia Specific Inclusion Criteria**

Clinical Diagnosis of AlzD made by a specialist\* in a patient who fulfils the NIA/AA criteria for Probable AlzD, specifically:

- Meets the criteria for dementia
  - The memory impairment and cognitive deficits cause significant impairment in social or occupational functioning, and represent a significant decline from a previous level of functioning, not explained by a delirium or a major psychiatric disorder
  - Impairment of at least two cognitive domains
- Insidious or gradual onset
- Clear history of worsening cognition by report or observation

- The initial and most prominent cognitive deficits are evident on history and examination in one of the following domains:
  - Amnestic: impaired learning and recall of recently learned information
  - Non amnestic: language/visuospatial/executive dysfunction
- No evidence of substantial cerebrovascular disease, core features of dementia with lewy bodies, features of frontotemporal dementia, prominent features of semantic variant primary progressive aphasia, evidence of active neurological disease, a non-neurological co-morbidity or medication that could affect cognition

*\*A specialist being defined as a psychiatrist or a geriatrician, or a specialist mental health nurse with a specific interest or expertise in cognitive disorders.*

#### **7.4 Exclusion Criteria**

- Male or Female, aged under 18 years
- Unable (in the Investigator's opinion) or unwilling to comply with any study requirements
- Female participants who are pregnant, lactating or planning pregnancy during the course of the study
- Major co-morbidity likely to affect cerebral autoregulation; severe respiratory disease, carotid artery stenosis, atrial fibrillation, severe cardiac failure (left ventricular ejection fraction <20%), extreme frailty or multi-morbidity.

## 8. STUDY PROCEDURES

### 8.1 Informed Consent and Assessment of Capacity

Following provision of study specific information, the potential research participant (Volunteer or Patient) will be able to contact the researcher with the contact details provided to confirm willingness to participate in the study. At this time an appointment will be made to attend the Leicester Royal Infirmary to undergo formal consent and capacity assessment as outlined below.

Participant consent form must be in place before the undertaking of any research project-specific assessments, using the current version (*Participant (Volunteer or Patient) Consent Form*) which has been approved by the National Research Ethics Service and the local Trust Research and Development Department. Written and verbal versions of the current approved Participant (Volunteer or Patient Information Leaflet, Participant (Patient or Volunteer) Consent Form or will be presented detailing no less than: the exact nature of the study; the implication and constraints of the protocol; the known side effects and any risks involved in taking part. It will be clearly stated that the participant is free to withdraw from the study at any time for any reason without prejudice to future care, and with no obligation to give the reason for withdrawal.

At the time of consent, the researcher will re-assess the patient's capacity in accordance with the Mental Capacity Act 2005. This is a 2 stage process where firstly, there must be a concern that the patient may lack capacity (in this case due to cognitive impairment). When the study information is provided to participants, it will be assessed in 4 steps. Firstly, the ability to understand the information, secondly to weigh up the information, thirdly to retain the information, and finally be able to communicate the decision back to the researcher. This initial discussion and assessment will take place at the outpatient memory clinic and stroke clinic at the LPT and UHL respectively.

The person who obtains consent and performs the capacity assessment must be suitably qualified and experienced, and have been authorised to do so by the Chief/Principal Investigator (CI/PI), as detailed on the Delegation of Authority and Signature log for the study. The original signed Informed Consent form will be retained at the study site within the Investigator Site File (ISF). A copy of the signed Informed Consent form will be given to

participants and a copy retained in the participant's medical notes For HC volunteers, the original signed copy will be retained within the ISF, and a copy provided to the volunteer.

A letter will be sent to the volunteer's and patient's GP informing them of their participation in the study (*GP Information Leaflet (Volunteer or Patient)*).

### **Process for Consent in Volunteers**

We will only invite volunteers who have capacity to give us consent in this research study. All potential volunteers will be recruited from departmental volunteers, patient's relatives and friends and by poster advertisement in the outpatient clinics at the University Hospitals of Leicester (UHL) NHS Trust. The researcher will explain the details of the research study and provide a Participant (Volunteer) Information Leaflet. The researcher will answer any questions or concerns that the volunteer has regarding participation in the study.

Volunteers will be allowed up to seven days to consider the information, and the opportunity to question the Investigator, their GP or other independent parties to decide whether they wish to participate in the study. Written informed consent will then be obtained by means of Volunteer dated signature and dated signature of the person who presented and obtained the informed consent.

Prior to the study, we will also ensure that the volunteer is aware that he/she is free to withdraw from the study at any time for any reason. However, should this situation occur the research team would like to keep all the health information and data that has been collected so far for the final analysis. This will be clearly stated in both the Participant (Volunteer) Information Leaflet and Participant (Volunteer) Consent Form.

### **Process for Consent in Patients**

We will only invite patients who have capacity to give us consent in this research study. All potential participants will be approached initially by the responsible clinical physician, who will undertake the eligibility screening and subsequently introduced to the research team member(s). The research team member(s) will explain the details of the research study and

provide a Participant (Patient) Information Leaflet. The researcher will answer any questions or concerns that the Participant (Patient) has regarding participation in the study.

The Participant (Patient) will be provided with the researcher's contact details, to allow up to 7 days to consider the information, and have the opportunity to question the Investigator, their GP or other independent parties to decide whether they wish to participate in the study. Written informed consent will then be obtained by means of participant dated signature and dated signature of the person who presented and obtained the informed consent. Capacity will be assessed as described above in accordance with the Mental Capacity Act 2005. If the patient expressed an interest in the study at the initial stage but did not make contact with the researcher, a follow-up reminder letter (*Patient Follow-up Letter*) will be sent to the patient through the direct care team with the researcher's contact details.

Prior to the study, we will ensure that the participant is aware that he/she is free to withdraw from the study at any time for any reason. However, should this situation occur we would like to keep all the health information and data that has been collected so far for the final analysis. This will be clearly stated in both the Participant (Patient) Information Leaflet and Participant (Patient) Consent Form.

## **8.2 TCD window insonation check**

Once a consent form has been signed, and before collecting baseline information on demographics, medical history, medications, and handedness, participants will undergo a brief Transcranial Doppler Ultrasound (TCD) check to ensure they have adequate acoustic temporal windows (inadequacy rates of 5-37% well documented in the literature) [Itoh et al 1993, Bos et al 2007, Marinoni et al 1997].

## **8.3 Collection of demographic data**

Baseline demographic data will be collected from the participants as detailed below:

### **Healthy controls**

- Demographics

Date of birth, gender, height, weight, and ethnicity will be recorded

- Medical History

Details of any relevant history of disease or surgical interventions will be recorded

Smoking status and weekly alcohol intake will be recorded

- Current Medications

Details of any prescription or over the counter medications will be recorded

- Handedness

Determined using the Edinburgh Handedness Inventory

### **Patients with MCI, VascD and AlzD**

- Demographics

Date of birth, gender, height, weight, and ethnicity will be recorded.

- Medical History

Details of any relevant history of disease or surgical interventions will be recorded

Smoking status and weekly alcohol intake will be recorded

Any family history of dementia will be recorded

- Current Medications

Details of prescription medication or over the counter medications will be recorded, including the use of any anti-dementia drugs

- Handedness

Determined using the Edinburgh Handedness Inventory [Oldfield et al, 1971]

In addition, the patient's medical records will be reviewed to extract the following information:

- Results and significant findings from Computerised Tomography (CT) head/Brain Magnetic Resonance Imaging (MRI), if undertaken
- Results and details of any previous cognitive testing
- Date of diagnosis of MCI, VascD or AlzD

#### **8.4 TCD Assessment**

For all subjects, all assessments will be undertaken in a dedicated cardiovascular research laboratory at Leicester Royal Infirmary (LRI), which is at a controlled temperature (20-24°C) and is free from distraction. Participants will be asked to refrain from heavy meals, strenuous exercise, alcohol, smoking and caffeine for four hours prior to attending the research laboratory. The subject will sit on an examination couch. Baseline casual BP will be calculated as a mean of three supine brachial BP readings using a validated UA767 BP monitor. Beat-to-beat non-invasive BP will be recorded continuously using the Finometer cuff device (Finapres Medical Systems; Amsterdam, The Netherlands) attached to the middle finger of the non-dominant hand. R-R interval will be recorded using a 3-lead ECG. End-tidal partial pressure of carbon dioxide (EtCO2) will be monitored using small nasal cannulae placed at the base of the nose (Salter Labs, ref 4000) attached to a capnograph (Capnocheck Plus) to monitor the breathing. Simultaneous bilateral insonation of the middle cerebral arteries (MCAs) will be performed using TCD with 2MHz probe using a Viasys Companion III, with the subject either sitting or lying supine on a couch (in the case of difficult to insonate windows). The vessel will be located via the temporal bone window, and identified as the MCA by the waveform, its depth, velocity, and the direction of flow. All parameters will be simultaneously recorded onto a computer software system (PHYSIDAS), providing data for subsequent off-line analysis. A head frame will be used to secure the ultrasound probes in position and to minimise their movement. Once satisfactory signals have been obtained, four recordings will be made:

- 1) A 5 minute baseline recording during which the patient sits quietly with their eyes open
- 2) A recording during which the participant undertakes the Attention, Memory, and Fluency tasks of the ACE-III Cognitive Examination.
- 3) A recording during which the participant undertakes the language tasks of the ACE-III Cognitive Examination.
- 4) A recording during which the participant undertakes the visuospatial ability, and final memory tasks, of the ACE-III Cognitive Examination.

During the recordings the internal plethysmography servo-adjust of the Finometer will be switched off, but this will be switched back on in between each recording to allow for accurate calibration of BP. A brachial BP will also be taken in between each recording using the same validated UA767 BP monitor as at the beginning of the baseline assessment. Recordings 2, 3 and 4 will each begin and end with a period of 1 minute baseline recording where the

participant sits quietly with their eyes open. An event marker will be used to mark the start of each individual question of the ACE-III, so that these can be identified within the recordings. Each individual question will be followed by a period of 1 minute rest, to allow CBFv to return to baseline levels. In order to ensure that visually impaired participants are not placed at a disadvantage during the cognitive examination, enlarged versions of the pictures contained within the ACE-III will be provided on A4 laminated cards.

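### Section 8.4 is inconsistent on posture and nothing requires posture to be recorded or held constant, so an imbalance between groups could not be detected and its effect on CBFv, beat-to-beat BP and ARI levels is unknown

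*Combined protocol and SAP*

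**What the plan says.** All the posture statements are in section 8.4.

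- Set-up: "The subject will sit on an examination couch".
- Casual BP, in the next sentence: "Baseline casual BP will be calculated as a mean of three supine brachial BP readings using a validated UA767 BP monitor".
- Insonation of the middle cerebral arteries: "with the subject either sitting or lying supine on a couch (in the case of difficult to insonate windows".
- Recording 1: "A 5 minute baseline recording during which the patient sits quietly with their eyes open".
- The 1-minute periods that open and close recordings 2 to 4: the "participant sits quietly with their eyes open". As with recording 1, no supine exception is given.
- BP between recordings: "A brachial BP will also be taken in between each recording using the same validated UA767 BP monitor". No posture is given.

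Section 8.5 provides for a repeat measurement in 11 participants after 3 months and does not mention posture. Controls are matched on age, gender and BP (sections 5.1 and 7.1), and section 7.2 also names co-morbidities. Neither posture nor window quality is a matching factor. Section 11.1 plans baseline comparisons and a repeated measures ANOVA, with no posture term and no sensitivity analysis.

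**The concern.** An operator following section 8.4 cannot tell what a participant insonated supine does during periods described as seated. Nor is it clear whether a seated participant lies down for BP between recordings. The casual BP is taken in a different posture from the seated recordings it accompanies.

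Window quality is a participant characteristic, and nothing balances it across groups. If supine recording were commoner in one group, any effect of posture on CBFv, beat-to-beat BP or ARI would be added to the group difference. Without a record of posture, this could be neither seen nor examined afterwards. The null hypothesis in section 11.1 covers the haemodynamic parameters themselves as well as their change during the ACE-III, so levels matter.

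The third secondary objective is reproducibility at 3 months. A change of posture between visits would be counted there as measurement variability.

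**Working it through.** **1. Which statements conflict.** The supine option for difficult windows can be read as an exception to a seated default. That reading does not explain the supine casual BP readings, which apply to everyone directly after the subject is seated. It also does not say how the recordings described as seated apply to a participant insonated supine. The between-recording BP has no stated posture at all.

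**2. Which comparisons are exposed.** Let B be a participant's baseline CBFv, D the rise during a task, and c an additive posture offset.

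- Posture constant in the session: the absolute change is (B + c + D) − (B + c) = D, so the offset cancels. The % change is 100·D/(B + c), so only the denominator is affected. A proportional offset cancels from % change exactly.
- Posture changed between baseline and task: the % change is 100·(D + c)/B, and the offset enters in full.
- Levels of CBFv, beat-to-beat BP and ARI: nothing cancels. The bias in a comparison of two groups is (difference in supine share) × (posture effect).
- Casual BP: supine for everyone as written, so posture does not confound that comparison between groups. Its fault is the mismatch with the seated recordings.

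**3. The plan's own figure, as a scale.** Section 11.2 states 11 per group for a 2-unit ARI difference, with 80% power at the 5% level. It gives no SD, so the figure can only be inverted. From n = 2·SD²·(1.960 + 0.842)²/2², n = 11 corresponds to SD ≈ 1.67 (two-sided, normal approximation). The two-sample t-test gives SD ≈ 1.59, which is used below.

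**4. Size under assumed values.** The documents give no posture effect and no supine share by group, so every gap and effect below is an assumption. With 11 per group, gaps of 10, 20 and 50 percentage points are about 1.1, 2.2 and 5.5 participants. Power is for a true 2-unit difference partly masked by the bias. The false-positive rate is for no true difference. Both are for one pairwise two-sided test at 5%, from the noncentral t distribution with standardised shift (2 − bias)/1.59 or bias/1.59.

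| Gap in supine share | Posture effect (ARI units) | Bias (units) | Share of 2-unit target | Power | False-positive rate |
|---|---|---|---|---|---|
| 10 points | 0.5 | 0.05 | 2.5% | 78.0% | 5.1% |
| 10 points | 1.5 | 0.15 | 7.5% | 73.6% | 5.5% |
| 20 points | 1.0 | 0.20 | 10% | 71.3% | 5.9% |
| 20 points | 1.5 | 0.30 | 15% | 66.4% | 7.1% |
| 50 points | 1.0 | 0.50 | 25% | 55.7% | 10.8% |
| 50 points | 1.5 | 0.75 | 37.5% | 41.8% | 18.3% |

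With equal supine shares the expected bias is zero. The table concerns ARI levels only; the documents give no figures from which to scale CBFv or beat-to-beat BP.

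**The case against.** The strongest reply is that section 8.4 describes a seated default with one stated exception, and that the planned task analysis is protected. Read naturally, the repeated measures ANOVA asks whether the change during the ACE-III differs between groups, and section 6.2 lists % change of CBFv. A posture offset held through the session largely drops out of both. This stands for within-person change, provided posture really is constant, which the protocol does not require. It does not cover levels of CBFv, beat-to-beat BP or ARI, or the repeat visit.

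Two further points also stand. Age and gender matching may narrow any difference in window quality. The CRF is not among the documents and may already have a posture field, although nothing in the protocol calls for one.

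A reader might go further and take the figure in section 8.2, "inadequacy rates of 5-37% well documented in the literature", as a supine rate, or take its 32-point width as a gap between groups. The documents do not support that. It is a range across published studies for inadequate windows, not for difficult ones, and it is not given by diagnosis. A reader might also infer that the supine casual BP is the reading used to match controls, so that matching is distorted. No section says which BP reading is used for matching.

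**Conclusion.** The inconsistency is in the current text and is more than missing detail, because the stated rule lets a participant characteristic set the posture and leaves no trace of it. Between-group levels of CBFv, beat-to-beat BP and ARI are open to a bias that could not be detected. The % change and reproducibility results are exposed if posture changes within a session or between visits.

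The size is unknown. Under the assumed gaps and effects above, and an ARI SD inferred from section 11.2, the bias runs from 0.05 to 0.75 ARI units, which is negligible to material. The upper end needs a large gap and a large effect together, and nothing in the documents points to either. The stronger conclusion, that patients will be supine more often than controls and that the trial's results will be confounded, does not follow from the text. The point is a risk that is cheap to remove.

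**What to change.** - Reconcile the posture statements in section 8.4.
- Use one posture per participant for all four recordings, the casual and between-recording brachial BP readings, and the repeat visit.
- Record posture on the CRF for each recording and BP reading, and report it by group.
- Repeat the main comparison without participants recorded supine, as a sensitivity analysis.
- Do not rely on a posture covariate in the main model. With 11 per group few participants are likely to be supine, and if posture follows group the two effects are hard to separate.

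One posture per participant does not itself balance the groups; it protects within-person change and makes any imbalance visible.

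The cost is wording, one CRF field and one analysis. Precision falls in the sensitivity analysis: if two of 11 were dropped from each group, the standard error would rise by a factor of √(11/9) = 1.11. Casual BP would no longer be supine for everyone, so it should be reported together with posture. The field must be in place before data collection, because unrecorded posture cannot be recovered.

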### **8.5 Follow-up measurements**

A sub-set of 11 Participants will be invited to return after 3 months to repeat the study measurement to assess for reproducibility. This will be stated explicitly on the consent form (*Volunteer and Patient consent forms*), but participants can decline to be contacted at this time, and can withdraw from the study at any time.

### **8.6 Definition of End of Trial**

The end of trial is the date of the last visit of the last participant.

At the end of the study, both healthy controls and patients will receive a written letter, in plain English, summarising the study findings and conclusions.

### **8.7 Discontinuation/Withdrawal of Participants from Study Treatment**

Each participant has the right to withdraw from the study at any time and without giving a reason. A decision to withdraw at any time, or a decision not to take part, will not affect the standard of care that participant receives. In addition, the investigator may discontinue a participant from the study at any time if the investigator considers it necessary for any of the following reason:

- An inability to comply with study procedures
- Consent withdrawn
- Loss of capacity

In the case of withdrawal in the healthy control group, they will be replaced to ensure that there are 11 healthy control subjects with complete data analysis.

All of the above will be recorded in the case report form (CRF).

Prior to the study, we will ensure that the participant is aware that he/she is free to withdraw from the study at any time for any reason. However, should this situation occur we would like to keep all the health information and data that has been collected so far for the final analysis. This will be clearly stated in both the Participant (Patient and Volunteer) Information Leaflet and Participant (Patient and Volunteer) Consent Form.

